#### Ankylosing Spondylitis Quality of Life (ASQoL) 8.3.5

The ASQoL consists of 18 items, each with a score of 0 = no or 1 = yes, so that the sum score ranges from 0 to 18, with higher scores indicating worse quality of life. The questionnaire is available in Section 12.11.

total score will be left missing. **8.3.6** If 3 or fewer items are missing, the missing responses will be imputed with the mean of the available responses from that visit to calculate a total score. If more than 3 items are missing, the

## Maastricht Ankylosing Spondylitis Enthesitis (MASES) Index

The MASES Index comprises 13 items (bilateral costochondral 1, costochondral 7, anterior superior iliac spine, posterior iliac spine, iliac crest and proximal insertion of the achilles tendon sites, and the fifth lumbar vertebral body spinous process) (Heuft-Dorenbosch et al, 2003) each

scored as 0 = yes or 1 = no and then summed for a possible score of 0 to 13, with higher scores indicating worse enthesitis. The questionnaire is available in Section 12.12.

variations thereof. If 7 or more items are available, MASES will be imputed by dividing the sum score with the number of assessments and multiplying the result with 13. If less than 7 times are available, MASES will be treated as missing.

Presence of enthesitis at Baseline should be defined as a Baseline MASES score >0.

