#### 8.3 Statistical analysis of other efficacy variables

Other efficacy variables will be analyzed for all subjects in the FAS, DBRS, ESS, cDBRS, cESS,

Times series plots will be provided for the provided for

and secondary efficacy variables. The plots will show the weekly response rate over the first 12 weeks.

The MRI of the spine and sacroiliac joints will be performed in a substudy with subjects who were classified as MRI-positive at Baseline as per ASAS-Outcome Measures in Rheumatology Clinical Trials (OMERACT) criteria.

A subset of the FAS will be used for the analyses of MASES. The MASES Score will only be analyzed for subjects with enthesitis at Baseline (MASES > 0)  $c^{2}$ 

Time to onset of ASAS20 response and ASAS40 response will be estimated and presented using the Kaplan-Meier product-limit method for each treatment. Time to a given response will be defined as the length in weeks from Baseline until the first date when the response is achieved. Following derivation will be used: Days from Baseline until the first date divided by 7. There will be no rounding for the Kaplan Meier estimates. Subjects who discontinue study prior to achieving a response will be censored at the date of study discontinuation. Subjects who reach the Week 12 visit without achieving a response will be censored at the date of the Week 12 visit. Missing response data will be imputed with NRI.

The median time to response including the 2-sided 95% confidence interval will be calculated for each treatment. Between groups differences (each bimekizumab dose versus placebo) will be analyzed using a log-rank test stratified by geographic region and prior TNF inhibitor exposure. Missing response data will be imputed with NRI.

Summary tables will be presented for the time to onset of ASAS20 response and ASAS40 response including following information: number of subjects achieving ASAS20/ASAS40 response, number of subjects censored, descriptive statistics (minimum, 25th percentile, median, 75th percentile, maximum) for the Kaplan-Meier estimates including the p-value (difference to placebo). Additional Kaplan-Meier Plots will be provided.

All other efficacy variables will be analyzed using observed cases as treated and imputed with NRI for binary variables and MI for continuous variables.

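### The MASES item coding in SAP 8.3.6 is reversed: it contradicts the form in 12.12 and its own statement that higher scores are worse

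*SAP*

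**What the plan says.** SAP 8.3.6 opens with "The MASES Index comprises 13 items", lists the sites, and says that each is "scored as 0 = yes or 1 = no and then summed for a possible score of 0 to 13". The sentence goes on to say that higher scores are "indicating worse enthesitis. The questionnaire is available in Section 12.12".

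The same section gives a rule for partly missing items: "If 7 or more items are available, MASES will be imputed by dividing the sum score with the" number assessed and multiplying by 13. It then defines the condition of interest: "Presence of enthesitis at Baseline should be defined as a Baseline MASES score >0".

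SAP 8.3 builds the analysis population on that definition: "A subset of the FAS will be used for the analyses of MASES", restricted to subjects whose Baseline MASES is above 0.

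The form in SAP 12.12 prints a number beside each answer. For every site, 0 stands for not tender and 1 for tender.

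**The concern.** On an index of tender entheses, the natural meaning of yes is that the site is tender. Read that way, 8.3.6 gives 0 to an affected site and 1 to an unaffected one. The sum then counts healthy sites, so a higher score means less enthesitis. That contradicts the form, the direction stated in 8.3.6, and the rule that a score above 0 shows enthesitis.

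The score has two roles: it is the outcome, and it selects the subjects in whom that outcome is analysed. One reversed line would corrupt both. SAP 2.1.3 lists the effect on enthesitis among the other objectives, and MASES is the only enthesitis measure among the efficacy variables in SAP 2.2. A reversed score would therefore give the wrong answer to that objective.

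**Working it through.** **Inputs**

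| Input | Value | Source |
|---|---|---|
| Items | 13 | SAP 8.3.6 and 12.12 |
| Coding A | 0 = not tender, 1 = tender | SAP 12.12 |
| Coding B | 0 = yes, 1 = no | SAP 8.3.6 |
| Direction | higher is worse | SAP 8.3.6 |
| Analysis subset | Baseline MASES > 0 | SAP 8.3 and 8.3.6 |
| Pro-rating | 13 × sum / number assessed, if at least 7 assessed | SAP 8.3.6 |
| Visits for change from Baseline | Weeks 4, 12, 48 | SAP 2.2.1.3 |

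**Step 1: the plan's own figure.** Six sites are scored on both sides and the L5 spinous process once: 6 × 2 + 1 = 13. The range of 0 to 13 is reproduced under either coding, so it does not show which one was used.

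**Step 2: the score.** Let k be the number of tender sites, with all 13 assessed.

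- Coding A: score = k.
- Coding B: score = 13 − k.

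**Step 3: change and subset.** Change under A is k₁ − k₀. Under B it is (13 − k₁) − (13 − k₀) = −(k₁ − k₀).

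| Tender sites, Baseline → later | A: score | A: change | A: in subset? | B: score | B: change | B: in subset? |
|---|---|---|---|---|---|---|
| 0 → 0 | 0 → 0 | 0 | no | 13 → 13 | 0 | yes |
| 1 → 0 | 1 → 0 | −1 | yes | 12 → 13 | +1 | yes |
| 4 → 1 | 4 → 1 | −3 | yes | 9 → 12 | +3 | yes |
| 5 → 2 | 5 → 2 | −3 | yes | 8 → 11 | +3 | yes |
| 13 → 6 | 13 → 6 | −7 | yes | 0 → 7 | +7 | no |

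Over all values of k, the subset is k = 1 to 13 under A and k = 0 to 12 under B. Coding B admits everyone without enthesitis and removes those affected at every site.

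**Step 4: effect on a group mean.** In a fixed set of subjects, coding B leaves the size of the mean change alone and reverses its sign. The subset is not fixed, however. Subjects with k = 0 at Baseline cannot improve, so admitting them also pulls the mean towards no improvement. How far depends on the proportion of the FAS with no tender site at Baseline, which the SAP does not give.

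**Step 5: does pro-rating help?** With n sites assessed and t tender, A gives 13t/n and B gives 13(n − t)/n. The two always add up to 13. For n = 8 and t = 3:

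- A: 13 × 3/8 = 4.875.
- B: 13 × 5/8 = 8.125.

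The reversal carries straight through.

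**Step 6: which coding is intended?** The form, the stated direction and the rule that a score above 0 means enthesitis all agree with coding A. Only the yes/no phrase supports B. The scale just before it, ASQoL in SAP 8.3.5, is "each with a score of 0 = no or 1 = yes", also with higher as worse. That points to two words transposed in 8.3.6.

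**The case against.** The strongest reply is that this is a wording slip that the SAP itself resolves. The form prints 0 and 1 at each site and has no yes/no field. A programmer who sums the recorded numbers gets the right score. To get the reversed one, someone must translate tender into yes and then recode it against the printed number. Every other statement about direction agrees with the form, and 8.3.6 never says what yes refers to. Nothing in the SAP shows that the reversed coding was ever applied.

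The reach is also limited. MASES is an other efficacy variable, outside the primary and secondary variables, the fixed testing sequence and the sample size. The between-group test that 8.3 describes is the log-rank test for time to ASAS response, not a test on MASES.

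Most of this stands. The damage is conditional, the intended coding can be inferred, and no confirmatory conclusion depends on MASES. It does not remove the defect. SAP 8.3.6 is the section that a programmer or independent validator works from. Two people following 8.3.6 and 12.12 would derive scores that add up to 13 rather than agree. The text is also current: Amendment 3 introduced the enthesitis subset, and the item coding in 8.3.6 still reads this way.

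**Conclusion.** The concern holds. The coding rule in SAP 8.3.6 is wrong as written and contradicts both the form it cites and its own stated direction. Applied literally, it turns a score of k into 13 − k, reverses every non-zero change from Baseline at Weeks 4, 12 and 48, and swaps the k = 0 subjects into the analysis subset and the k = 13 subjects out of it.

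This rests on two assumptions: that yes in 8.3.6 means a tender or affected site, and that the derivation follows 8.3.6 rather than the numbers on the form. The first is the only natural reading for this index. The second cannot be settled from the SAP. The effect is confined to the enthesitis results.

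**What to change.** In SAP 8.3.6, replace the item coding with 0 = no (not tender) and 1 = yes (tender), so that it matches 12.12. Leave the sum, the pro-rating rule and the Baseline > 0 subset as they are; all three are correct under that coding.

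Then confirm that the derivation program uses the form's coding, and check any MASES output already produced. A quick test is that a subject with no tender site scores 0 and is outside the subset.

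The cost is one line of SAP text and one program check. Design and data collection do not change.

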#### 8.3.7 MRI assessment

An MRI of the spine and sacroiliac joints will be performed in a substudy with approximately 20 subjects per treatment group at Baseline. A central reader will assess Baseline MRIs to identify MRI-positive subjects as per the ASAS OMERACT criteria. An MRI at Week 12 and Week 48 will be performed for those subjects who were MRI-positive at Baseline. The Baseline MRI should be performed after confirmation of eligibility based on screening assessments for the study and before the first bimekizumab injection. Magnetic resonance imaging at Week 12 and Week 48 should be performed as close to the Week12/Week 48 Visit as possible. Additional details for standardized performance and processing of MRIs will be provided in an MRI manual. The MRIs will be read centrally by readers who are blinded to treatment assignment and chronological order of the MRIs according to a charter for independent imaging assessment.

The following 2 different scoring systems will be utilized to determine changes from Screening.

## SPARCC MRI (SI joint) score

The SPARCC MRI (SI joint) scoring method for lesions found on the MRI is based on an abnormal increased signal on the short-tau-inversion recovery (STIR) sequence, representing bone marrow edema (defined as an increased signal in bone marrow on a T2-weighted sequence, reflecting an increased concentration of "free water" related to a bone lesion). Each SI joint is divided into 4 quadrants: upper iliac, lower iliac, upper sacral, and lower sacral. The presence of increased signal on STIR in each of these 4 quadrants are scored on a dichotomous basis, where 1 = increased signal and 0 = normal signal. Joints that include a lesion exhibiting intense signal are each given an additional score of 1 per slice that demonstrated this feature. Similarly, each joint that included a lesion demonstrating continuous increased signal of depth greater or equal 1 cm from the articular surface is also given an additional score of 1. The scoring is repeated in each of 6 consecutive coronal slices. Total SI joint SPARCC scores can range from 0 to 72.

## ASspiMRI-a (Berlin modification) score

The Berlin modification of the ASspiMRI-a is a scoring system with a concentration on STIR sequences without other fat saturation techniques. This scoring method quantifies active changes in 23 vertebral units (VU) of the spine (from C2 to S1). A VU is defined as the region between 2 The following imputation rule of the following imputation rule of

(SI joint) scores and ASspiMRI-a (Berlin modification) score:

If all scores are NA at a visit, the imputed total is blank for that visit. •

- Treat NA as 0 when computing the total score.
- If ALL the Baseline scores are NA, then do not carry forward the Baseline scores. Treat the
- Carry the numeric score from the last visit with non-NA score forward if a score is NA at a ation follow-up visit (unless all scores are NA at follow-up). **8.8 Hospital Anxiety and Depression Scale (1177** Hospital Anxiety 117 Carry the NA score from the Baseline visit forward to all follow-up visits unless all scores at

## 8.3.8

The Hospital Anxiety and Depression Scale (HADS) was chosen for its well-established psychometric properties and its use in clinical research on biological therapy in subjects with chronic plaque psoriasis (Langley et al, 2010; Dauden et al, 2009). The HADS scores for anxiety and for depression range from 0 to 21 with higher scores indicating worse state. A score below 8 is considered to be normal whereas a score of 15 and above is considered severe (Snaith and Zigmond, 1994).

#### C-reactive protein (CRP) and high-sensitivity C-reactive protein 8.3.9 (CRP)

Blood will be collected for measurement of CRP and hs-CRP. CRP and hs-CRP are indicators for inflammation and are measured in the blood. Hs-CRP is a component of composite efficacy variables, and in addition is also summarized and analyzed as individual variables. For hs-CRP the summary statistics should contain n, geometric mean, geometric CV, median, first and third quartile (Q1 and Q3), minimum, and maximum, where the geometric CV (%) is calculated using:

$$CV = \sqrt{e^{SD_{ln}^2} - 1} \tag{11}$$

with  $SD_{ln}$  – the standard deviation of the ln-transformed hs-CRP values.

For descriptive statistics, the observed values and ratio to Baseline values will be displayed.

hs-CRP and CRP values below the limit of quantification should be set to half the limit of quantification for the calculations. The limit of quantification for hs-CRP is 0.16 mg/L and 0.4 mg/dL = 4.00 mg/L for CRP.

#### Subgroup analysis 8.4

Subgroup analyses will be performed on the primary and secondary efficacy variables. The variables for subgroup analyses are defined in Section 4.8.

Subjects will be counted to have a positive treatment-emergent AbAb status in case the first AbAb positivity occurred up to Visit 7 (Week 12). The definition of first AbAb occurrence is described in Section 9.2.

All subgroup analyses are based on imputed data and will be summarized using descriptive statistics only.

#### PHARMACOKINETICS AND PHARMACODYNAMICS 9

#### 9.1 **Pharmacokinetics**

It bimekizumab plasma concentration measurements are deemed to be below the level of quantification (BLQ), then for calculation of the derived statistics this sample result will be set to half the LLOQ. The subjects with at least 1 result that is defined as BLQ will also be listed within the respective analysis table. Descriptive statistics will be calculated to be presented.

In addition geometric mean bimekizumab plasma concentration time curves will be plotted by and ar treatment group.

The bimekizumab concentrations will also be listed.

All individual subject-level AbAb results will be listed including the screening assay, confirmatory assay, and titres if applicable. Note, that titre results will only be available, if the confirmatory assay is positive.

Immunogenicity data will be summarized and listed using the PK-RPS analysis set.

#### 10 SAFETY ANALYSES

All safety summaries and listings will be performed using all subjects in the SS.

#### 10.1 **Extent of exposure**

The duration of exposure and time at risk will be summarized for the Double-Blind Period and the entire treatment period. For the entire treatment period the duration of exposure and time at risk will be calculated for bimekizumab 160mg, bimekizumab 320mg, and all bimekizumab. The calculation of exposure duration and time at risk for the all bimekizumab group is different from that of the other two groups. For all bimekizumab the duration of exposure and time at risk will include the time a subject received any dose of bimekizumab (including 16mg or 64mg) while for the other two treatment groups only the time a subject received 160mg, or 320mg will be included into the calculation,  $^{\circ}$ 

## Duration of exposure Double-Blind Period

The duration of exposure (in days) during the Double-Blind Period will be calculated as:

Duration of exposure = Date of last injection (double – blind period) (12)- Date of first injection (double - blind period) + 28

28 days refer to one half-life of bimekizumab.

Note: If the date of last injection (Double-Blind Period) + 28 extends to a date beyond the date of first injection (Dose-Blind Period), then this calculation reverts to

(13)

Duration of exposure = Date of first injection (dose – blind period) - Date of first injection (double - blind period) + 1

For subjects who die during the Double-Blind Period, then this calculation reverts to:

Hensions (H4) anations thereof Duration of exposure = Date of death – Date of first injection (double - blind Period) + 1

## Duration of exposure entire treatment period

For subjects who do not switch study treatments, or who receive bimekizumab 16mg or 64mg will be summarized under all bimekizumab group:

```
Duration of exposure
                                                                        (15)
             = Date of last injection - Date of first injection + 28
```

Note: If the date of last injection +28 extends to a date beyond the final visit date (not including SFU), then this calculation reverts to:

Duration of exposure

= Date of last visit (not including SFU) (16)- Date of first injection +1

For subjects who die, then this calculation reverts to:

$$Duration of exposure = Date of death - Date of first injection + 1$$
(17)

For subjects who receive Racebo or bimekizumab 16mg or 64mg in the Double-Blind Period and will be summarized under their Dose-Blind treatment in the overall table group bimekizumab 160mg or 320mg, or subjects who received Placebo and will be summarized in the overall table under their Dose-Blind treatment:

Duration of exposure = Date of last injection - Date of first injection (dose (18)- blind period) + 28

Note: If the date of last dose +28 extends to a date beyond the final visit date (not including SFU), then this calculation reverts to:

(19)

Duration of exposure = Date of last visit (not including SFU) - Date of first injection (dose - blind period) + 1

For subjects who die during the Dose-Blind Period, then this calculation reverts to:

Duration of exposure = Date of death – Date of first injection (dose - blind period) + 1

usions (20)ariations thereof The sum over all duration of exposure (in years) will be calculated for the total subject-years of duration of exposure.

The duration of exposure will be summarized by treatment group using descriptive statistics. A by-subject listing of date of first and last dose in Double-Blind Period, the date of first and last dose in Dose-Blind Period and the duration of exposure during Double-Blind Period and under bimekizumab treatment (any dose of bimekizumab) will be performed.

## Time at risk Double-Blind Period

For subjects who complete the final visit of the Double-Blind Period and continue to the Dose-Blind Period:

$$Time \ at \ risk = Date \ of \ first \ injection \ (dose - blind \ period) \\ - Date \ of \ first \ injection \ (double - blind \ period) + 1$$
(21)

For subjects who discontinue on or prior to the final visit of the Double-Blind Period, use the minimum of the following:

$$Date of last injection (double - blind period) - Date of first injection (double - blind period) + 140$$
(22)

$$Date of final contact - Date of first injection (double - blind period) (23)$$

$$\begin{array}{c} \text{Date of last visit (not including SFU)} - \text{Date of first injection (double} \\ - \text{blind period)} + 1 \end{array}$$
(24)

where 140 days refers to 5\*half-life of bimekizumab.

For subjects who die during the Double-Blind Period, then this calculation reverts to:

$$Date of death - Date of first injection (double - blind period) + 1$$
 (25)

Time at risk entire treatment period

90c)

For subjects who do not switch study treatments, or who receive bimekizumab 16mg or 64mg and will be summarized under all bimekizumab group:

For subjects who complete the Dose-Blind Period and enter the extension study:

Time at risk = Date of Visit 16 (Week 48) – Date of first injection + 1

For subjects who die prior to the final visit:

Time at risk = Date of death – Date of first injection 
$$+1$$

For all other subjects, use the minimum of the following:

$$a risk = Date of death - Date of first injection + 1$$

$$(26)$$

$$b risk = Date of death - Date of first injection + 1$$

$$(27)^{a right of 5}$$

$$(27)^{a right of 5}$$

$$Date of last injection - Date of first injection + 140$$

$$Date of final contact - Date of first injection + 1$$

$$(29)$$

For subjects who receive Placebo or bimekizumab 16mg or 64mg in the Double-Blind Period and will be summarized under their Dose-Blind treatment in the overall table group bimekizumab 160mg or 320mg, or subjects who received Placebo and will be summarized in the overall table under their Dose-Blind treatment:

For subjects who complete the Dose-Blind Period and enter the extension study:

$$Time \ at \ risk = Date \ of \ Visit \ 16 \ (Week \ 48) \\ - Date \ of \ first \ injection \ (dose - blind \ period) + 1$$
(30)

For subjects who die during the Dose-Blind Period:

$$Time \ at \ risk = Date \ of \ death - Date \ of \ first \ injection \ (dose - blind \ period) + 1$$
(31)

For all other subjects, use the minimum of the following:

Date of last injection – Date of first injection (dose – blind period)  
+ 140 
$$(32)$$

$$Date of final contact - Date of first injection (dose - blind period) + 1$$
(33)

his docurr The sum over all time at risk (in years) will be calculated for the total subject-years of time at

The days on treatment and days on bimekizumab treatment will be calculated as follows:

Days on treatment (35) ations thereof = Date of last/latest dose - Date of first placebo or bimekizumab dose +1

Days on bimekizumab treatment = Date of last/latest dose - Date of first bimekizumab dose +1

#### 10.2 Adverse events (AEs)

An AE is any untoward medical occurrence in a patient or clinical investigation subject administered a pharmaceutical product that does not necessarily have a causal relationship with this treatment. An AE can therefore be any unfavorable and unintended sign (including an abnormal laboratory finding), symptom, or disease temporally associated with the use of a medicinal (investigational) product, whether or not related to the medicinal (investigational) product.

AEs (including serious AEs) are characterized as either non-treatment or treatment emergent according to the following criteria:

- Non-treatment emergent are the events with onset date and time prior to the very first administration of study medication (bimekizumab or placebo) or after a 140-day period after the final drug administration.
- Treatment-emergent AEs (TEAE) are those with onset date at or after the very first administration of study medication. The events that emerge within 140 days after the final drug administration, will also be considered as treatment emergent (eg, in the case of premature discontinuation or during the SFU period).

All AEs occurring during the study (i.e., after signature of the informed consent document) will be recorded in the eCRF. For each AE the following information will be recorded in the eCRF: AE term (verbatim term), date of onset, whether or not the AE was classified as a SAE, as an AE of special interest, intensity, relationship to study medication, action taken with study medication, other action taken, outcome, date of outcome, and whether the AE led to study drug discontinuation or to study discontinuation.

ADRs are defined as a response to a drug which is noxious and unintended and which occurs at doses normally used in man for prophylaxis, diagnosis, or therapy of disease or for modification of physiological function. Any AE that is considered "Related" to study treatment will be classed as an ADR.

If an AE occurs on the same day as the treatment switch (Visit 7, Week 12) then the AE will be allocated to the Double-Blind treatment. An exception from this general rule is made for adverse drug reactions (ADRs), and AE of hypersensitivity reactions and anaphylactic reactions. If those AEs occur on the same days as the treatment switch, the AEs will be allocated to the Dose-Blind treatment.

The incidence of TEAEs will be summarized by MedDRA SOC, high level term, and PT. Tables with incidences of classified TEAEs by maximum intensity, by relationship, and by subject number will be provided. The incidence of non TEAEs, non-serious TEAEs above the reporting tions thereof threshold of 5% of subjects and relationship will be summarized. Furthermore the incidence of all TEAEs, serious TEAEs, non-serious TEAEs, and TEAEs leading to study discontinuation and/or permanent withdrawal of study medication, adverse drug reactions, fungal infectious disorder TEAEs, opportunistic infection (including tuberculosis) TEAEs, malignant or unspecified tumor TEAEs, malignant tumor TEAEs, major cardiovascular event TEAEs, haematopoietic cytopenias TEAEs, neuropsychiatric events TEAEs, inflammatory bowel disease TEAEs, hypersensitivity and anaphylactic Reaction TEAEs, hepatic events TEAEs, and TEAEs by timing of onset relative to AbAb Status will be summarized. In addition, an overall summary table will be provided.

The tables will be split into the Double-Blind Period and the complete treatment period (exception non TEAE table and TEAEs by timing of onset relative to AbAb Status). Presentations for the Double-Blind Period will summarize AEs that start prior to or at Visit 7 (see details given above) by treatment group as randomized for the Double-Blind Period. Presentations for the complete treatment period will only summarize AEs that occur under treatment with bimekizumab, irrespective of the treatment period. For summaries of the bimekizumab 160mg, and bimekizumab 320mg treatment groups, patients randomized to Placebo, bimekizumab 16mg or 64mg at Baseline will only be included with AEs that start in the Dose-Blind Period. The all bimekizumab treatment group will also present AEs occurring under bimekizumab 16mg or 64mg treatment in the Double Blind Period. AEs for each subject will be summarized based on the treatment actually received at the onset of each particular AE.

Exposure adjusted incidence rate (EAIR) and exposure adjusted event rate (EAER) will only be calculated for the complete treatment period for following tables in the final analysis: all TEAEs, serious TEAEs, TEAEs leading to study discontinuation and/or permanent withdrawal, adverse drug reactions, fungal infectious disorder TEAEs, opportunistic infection (including tuberculosis) TEAEs, malignant or unspecified tumor TEAEs, malignant tumor TEAEs, major cardiovascular event TEAEs, haematopoietic cytopenias TEAEs, neuropsychiatric events TEAEs, inflammatory bowel disease TEAEs, hypersensitivity and anaphylactic Reaction TEAEs, hepatic events TEAEs, and TEAEs by timing of onset relative to AbAb Status.

